7 DISCONTINUATION OF STUDY INTERVENTION AND PARTICIPANT DISCONTINUATION/WITHDRAWAL

7.1 Discontinuation of Study Intervention

A participant may decide to permanently discontinue study medication for any reason at any time or the CMOG clinician may decide to permanently discontinue a participant from study medication. If study intervention is permanently discontinued, the participant will be scheduled for a final Virtual Visit to complete all Virtual Visit 2 study procedures or obtain sufficient medical and medication history to determine a final use outcome if all Virtual Visit 2 assessment procedures cannot be completed. See the SoA for data to be collected at Virtual Visit 2.

Note that discontinuation from study intervention is NOT the same thing as a withdrawal from the study.

If a participant decides to permanently discontinue study medication and their last TASS assessment was “OK to Use” or “Ask a Doctor” and indicated the doctor gave them permission to continue treatment, the participant will complete a final TASS at Virtual Visit 2. However, participants will not be required to complete the study mandated LDL-C retest.

While a study participant may decide to discontinue study medication at any time, the only events that would result in study medical personnel instructing the participant to stop taking rosuvastatin are “Stop Use” criteria (which the participant has not self-identified and taken the action to stop use) as listed below:

- Pregnancy
- Severe and unexplained muscle pain, tenderness, or weakness
- Symptoms of liver problems (upper belly pain, dark urine, yellowing of skin or whites of eyes)

If such a situation occurs, the participant's disposition will be classified as "Pregnancy" for this "Stop Use" warning or "Adverse Event" for Severe and unexplained muscle pain, tenderness or weakness or symptoms of liver problems "Stop Use" warnings. The participant will be scheduled for a Virtual Visit 2. All procedures will be performed except a final TASS and a study mandated test for LDL-C.

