The eDiary will be used to gather minimal data in an unbiased manner and is not used to instruct the participant on the proper use of the drug. The information gathered will include dosing (date/time and amount of drug taken), AEs (changes in health), and medication changes. The participant will record the unique ID from the study drug bottle to confirm receipt of the product.

The eDiary provider will provide a notification to the study team when they detect no activity in the eDiary for more than 7 days. This will generate a communication to the participant from the study staff to determine if (a) the participant has any questions about using the eDiary (re-training may be necessary) or (b) to understand if the participant is still participating in the study. No additional information will be provided beyond the original study instructions for the diary.

At the 60-day and 120-day planned telephone contacts, the eDiaries will be reviewed to determine if “Stop Use” criteria are present and to ask about any changes in health. If so, the CMOG clinician will discuss the entry with the participant to determine if it meets the “Stop Use” definition. Meeting the second co-primary endpoint and the secondary endpoint with regard to “Stop Use” warnings requires that the participant identify the “Stop Use” warning. Therefore, should a “Stop Use” warning be identified during the 60 or 120-day touchpoint, the participants will be managed as follows:

- If during the 60 or 120-day touchpoint, the participant volunteers that they had a stop use warning, they will be scheduled for Virtual Visit 2. Participants who self-identify a “Stop Use” criterion will complete all Virtual Visit 2 procedures including a TASS assessment.

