- If, on the other hand, the CMOG becomes aware of a “Stop Use” criterion during the telephone call that the participant did not identify, all Virtual Visit 2 procedures except a participant TASS and study mandated test for LDL-C will be performed. The reason for not repeating the TASS is that the participant did not self-identify the “Stop Use” criterion. Instead, the CMOG identified the criterion and discussed with the participant, which could bias the participant’s behavior when completing the TASS. For example, a participant who did not realize they should have stopped drug because of severe muscle symptoms, may answer “yes” to this question in the TASS and be categorized as a correct selector when, in reality, they may have answered “no” to this question if they had not spoken to a CMOG clinician prior to completing the TASS. Because the study staff had to

inform the participant that they met a “Stop Use” criterion, they will be considered a failure when evaluating the second co-primary endpoint related to “use”.

- Participants who the CMOG clinicians identify as having experienced “Stop Use” criteria are considered “Discontinued from Study Intervention” and not a withdrawal (refer to Section 7.1). In general, the only events recorded in an eDiary or communicated to the study staff during a phone check that would result in study medical personnel instructing the participant to stop taking rosuvastatin are “Stop Use” criteria. If such a situation occurs, the participant will be classified as a discontinuation from study intervention due to “Adverse Event” or “Pregnancy” and scheduled for a Virtual Visit 2.

If a participant records a “Do Not Use” warning in their eDiary, we will not contact them. Our intent in the AUS is to keep interactions with the participants to a minimum so we do not influence the participant’s behaviors or bias the outcome of the study. By doing this, we allow the real-life behavior to continue into the next reorder, at which time, the TASS reorder assessment would result in a “Crestor OTC is no longer right for you” message along with a message to stop drug and contact a doctor. In the AUS, the participant will also be messaged to contact the call center to schedule Virtual Visit 2.

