A participant may be discontinued from the study intervention by the CMOG at a scheduled follow-up phone call or eDiary review if the participant has not already identified the following conditions and stopped study drug: pregnancy; severe and unexplained muscle pain, tenderness or weakness; and symptoms of liver problems (upper belly pain, dark urine, yellowing of skin or whites of eyes). Note that discontinuation from study intervention is NOT the same thing as a withdrawal from the study. If such a situation occurs, the participant’s disposition will be classified as “Pregnancy” for this “Stop Use” warning or “Adverse Event” for severe and unexplained muscle pain, tenderness or weakness, or symptoms of liver problems. In these instances, the participant will be scheduled for a Virtual Visit 2 and all procedures will be performed except a final TASS assessment and a study mandated test (SMT) for LDL-C. In these situations, the final TASS assessment will be considered “Incorrect” since the participant did not identify the condition and stop medication. If the participant identifies the condition and stops medication on their own, they will be scheduled for Virtual Visit 2 and all procedures including the final TASS assessment will be performed.

The PP population includes participants that have completed the study. “Completed” means the participant completed the study if he/she has completed all phases of the study, including Virtual

Visit 2. “Completed” also includes participants that have discontinued with sufficient medical and medication history information and, when necessary, a verified LDL-C value collected prior to stopping the study in order to determine a final use outcome and has not withdrawn from the study. The goal is to have 100 limited literacy participants in the trial.

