3.2.6 Stop Use Warnings

Prior to every drug reorder, participants are required to enter the Web App and take an abbreviated medical reorder assessment. If a participant identifies a "Stop Use" warning, they are instructed by the Web App to both stop use and contact a doctor and will no longer be able to order drug. Stopping use can be ensured through the Web App by preventing participants from reordering medication; however, the participant must take the initiative to contact a doctor.

While the information used to assess stopping use can come from either the Web App or the Targeted Medical and Medication History Form at Virtual Visit 2, the information used to assess contacting a doctor will come from the Targeted Medical and Medication History Form completed by the clinician at Virtual Visit 2.

There are two “Stop Use” warnings for non-prescription rosuvastatin: (1) severe and unexplained muscle pain, tenderness, or weakness and (2) symptoms of liver problems (upper belly pain, dark urine, yellowing of skin or whites of eyes).

While some individuals may identify these symptoms and have treatment stopped through the use of the Web App, there is a reasonable probability that people with these symptoms will simply stop therapy and decide not to use the Web App because they do not want to reorder medication. Meeting the second co-primary endpoint and the secondary endpoint with regard to “Stop Use” warnings requires the participant to identify the “Stop Use” warning on their own. If during the planned 60- and 120-day touchpoint, following review of the eDiary, or through an unplanned contact from the participant, a “Stop Use” criterion is identified, the participants will be managed as follows:

- If during the interview with the clinician, the participant volunteers that they had a “Stop Use Warning”, they will be scheduled for Virtual Visit 2. Participants who self-identify a “Stop Use” criterion will complete all Virtual Visit 2 procedures including a TASS assessment.

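### One Stop Use rule requires the condition to be identified and the drug stopped, another only that it be identified, so a volunteer still taking drug can be scored two ways on co-primary 2.

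*Protocol*

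**What the plan says.** Four sections govern a Stop Use condition that comes up during the use period.

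- **Protocol 7.1.** Staff tell a participant to stop for Stop Use criteria "which the participant has not self-identified and taken the action to stop use". The Visit 2 that follows is reduced: "All procedures will be performed except a final TASS and a study mandated test for LDL-C".
- **SAP 3.1.** The same two-part condition governs discontinuation by the CMOG clinician. The final TASS is then counted as Incorrect, with the reason given that the participant did not both identify the condition and stop. The contrasting case reads: "If the participant identifies the condition and stops medication on their own, they will be scheduled for Virtual Visit 2", with a final TASS included.
- **Protocol 8.1.** If, at the day-60 or day-120 contact, "the participant volunteers that they had a stop use warning, they will be scheduled for Virtual Visit 2". That visit is then run in full, with a participant TASS. Having stopped is not a condition. A participant whose criterion is found by the CMOG gets no TASS and fails co-primary 2.
- **SAP 3.2.6.** The same rule, opening "If during the interview with the clinician, the participant volunteers that they had a" Stop Use warning, extended to eDiary review and unplanned contacts.

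SAP 3.2.3.3 uses the last earlier TASS as the participant outcome when the participant did not self-identify the criterion and was directed to stop. SAP Appendix B gives the final scoring by scenario.

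**The concern.** The two pairs of sections sort the same contact by different tests: identified and stopped, or identified alone. They part for someone who names the Stop Use warning on the call and is still taking the drug. Whether that person takes a final TASS, and whether co-primary 2 is Incorrect by rule or open to comparison, depends on which section the clinician and coders follow.

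Three things are at stake. A co-primary classification is not fixed by the plan. The Stop Use secondary endpoint counts those who self-identify and stop, without saying whether stopping after the call qualifies. And the volunteer rule does not mention whether staff instruct the participant to stop, although Protocol 8.1 treats prompt stopping as critical for these conditions.

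**Working it through.** **Step 1. Apply each rule to one participant**, who volunteers the Stop Use warning on the day-60 call and is still taking drug.

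| Question | Protocol 7.1 and SAP 3.1 | Protocol 8.1 and SAP 3.2.6 |
|---|---|---|
| Test | identified and stopped | identified |
| Met? | no | yes |
| Final TASS at Visit 2 | no | yes |
| Co-primary 2 | Incorrect (stated in SAP 3.1 only) | decided by comparison with the CMOG outcome: Correct, Incorrect or Mitigated |
| Staff instruct stopping | yes | volunteer bullet is silent |

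**Step 2. See whether another section settles it.** In Appendix B, the row for a participant who does not stop use assumes the warning was not identified. The rows for those who identify it and complete the assessments allow all three scores and do not ask when the drug was stopped. SAP 3.2.3.3 leans towards identification alone, because its earlier-TASS rule is keyed to not self-identifying. Neither place resolves the case.

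**Step 3. Reproduce the plan's figure for co-primary 2.** Inputs from Protocol 9.1 and 9.2: n = 500, true rate 90%, success if the two-sided 95% Clopper-Pearson lower bound exceeds 85%, stated power at least 90%.

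- Lower bound for x correct: L(x) = 0.025 quantile of Beta(x, 500 − x + 1).
- L(440) = 84.82% and L(441) = 85.04%, so the pass mark is 441/500 = 88.2%.
- Power = P(X ≥ 441 | 500, 0.90) = 0.919. One-sided type I error at 85% = 0.0235.

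The stated power reproduces. No figure in the plan is wrong.

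**Step 4. Effect on co-primary 2.** One reclassified participant moves the rate by 1/500 = 0.2 points. The number k is not in the documents; 0 to 10 is assumed. Starting from 450/500:

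| k moved to Incorrect | Correct | Lower bound | Power if the true rate is 0.90 − k/500 |
|---|---|---|---|
| 0 | 450 | 87.0% | 0.919 |
| 1 | 449 | 86.8% | 0.894 |
| 2 | 448 | 86.6% | 0.863 |
| 5 | 445 | 85.9% | 0.744 |
| 9 | 441 | 85.04% | 0.535 |
| 10 | 440 | 84.8% | 0.480 |

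Ten reclassifications would turn a pass at 450 into a fail; a result close to 441 would need fewer.

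**Step 5. Effect on the Stop Use secondary.** The denominator is the number of participants the CMOG identifies as having a Stop Use warning. Assume 1% to 5% of 500, that is 5 to 25. One case then moves the percentage by 100/25 = 4 to 100/5 = 20 points.

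**The case against.** The strongest reply is that this is a narrow wording mismatch affecting very few people. Much of that stands.

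- **Stop instruction.** A reader might infer that the sections give opposite instructions on stopping. They do not. The volunteer bullet is silent; it does not tell staff to hold back. The third bullet of that list says Stop Use criteria communicated on a phone check lead staff to instruct stopping, and is not expressly limited to non-volunteers. Protocol 8.4.4 refers participants with symptoms suggesting severe myopathy, rhabdomyolysis or liver injury for immediate care, and 8.4.7.1 covers pregnancy. This part is an ambiguity.
- **Automatic credit.** A reader might infer that Protocol 8.1 scores the volunteer Correct. It makes Correct possible; the comparison decides.
- **Symptom only.** Someone who reports severe muscle pain without recognising it as a Stop Use warning resembles the protocol's own example of a criterion found by the CMOG, and already fails. The conflict is confined to someone who names the warning.
- **Bias.** Protocol 8.1 withholds the TASS because prior discussion is something "which could bias the participant’s behavior when completing the TASS". That reason is given for criteria the CMOG found and raised. The volunteer also takes the TASS after clinician contact, but the protocol does not say that it is biased.
- **Which test should score.** Protocol 3.1 lets co-primary 2 be met by identifying a health change in the Web App or by acting in line with the label. A participant still taking drug who enters the symptom at reorder gets Do Not Use and can score Correct. The documents therefore do not establish that identified but not stopped must be Incorrect.
- **Timing.** SAP 4.2.4 already describes days from warning to stopping, and Protocol 3.1 sets no success threshold for the warning endpoints.

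None of this removes the difference between the two tests, which appears in both documents.

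**Conclusion.** The conflict is real. Protocol 7.1 and SAP 3.1 use identified and stopped; Protocol 8.1 and SAP 3.2.6 use identified alone; Appendix B has no row for the participant on whom they differ. That participant is Incorrect by rule under one pair and may be Correct under the other. This rests on reading the joining word in 7.1 and SAP 3.1 as a two-part condition, which SAP 3.1's stated reason for Incorrect supports.

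The size is unknown and probably small: Protocol 3.1 expects warning events to be infrequent, and volunteers still taking drug are only a subset of them. The effect on co-primary 2 is slight unless the result is near the pass mark. The Stop Use secondary is more exposed because its denominator may be small. The documents support a request to reconcile the rules. They do not support a claim that staff are given opposite stop instructions, or that one scoring rule is plainly right.

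**What to change.** Before database lock:

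1. Reconcile Protocol 7.1 and 8.1 with SAP 3.1, 3.2.3.3 and 3.2.6, so that one test decides whether a final TASS is taken and how co-primary 2 is scored.
2. Add an Appendix B row for a participant who has identified the warning but not yet stopped, with the score that follows from that test. Check it against the handling of a participant still taking drug who enters the same symptom at reorder.
3. State whether stopping after the contact counts for the Stop Use secondary, and how imputed stop dates are treated. Appendix F places many month-only stop dates halfway between the event and the month's end, which cannot reliably show whether stopping came before or after a call.
4. Report co-primary 2 and the Stop Use secondary under the other reading as a sensitivity analysis.
5. Make the text on when staff act consistent across these sections. The sponsor decides the clinical rule.

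The cost is wording in two protocol sections and three SAP sections, one Appendix B row, a sentence on the secondary endpoint and one sensitivity analysis. Stop dates are already collected on the Visit 2 history form, although some will be partial. A few participants may move from Correct to Incorrect.

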8.2 Efficacy Assessments

The efficacy of nonprescription rosuvastatin will be assessed as a co-primary endpoint and in **CCI** [REDACTED] During the use period of the study, participants will be told to retest their LDL-C. For those who do not retest or have unverified source for the LDL-C data inputted into the Web App, a study mandated test will be required for Virtual Visit 2 for those participants described in Section 8, Step 22. The LDL-C data will be used to assess the overall response to treatment.

8.3 Safety Assessments

Planned time points for all safety assessments are provided in the SoA.

8.3.1 Physical Examinations

There will be no physical examinations performed as part of this study.

8.3.2 Vital Signs

Blood pressure measurement will be provided at study entry and may be performed through a local testing site (e.g., retail-based BP kiosks) if the subject did not provide a verified source. See Section 8, Step 6 for further details.

8.3.3 Electrocardiograms

No ECGs will be performed as part of this study.

8.3.4 Clinical Safety Laboratory Assessments

At Virtual Visit 1, if the subject cannot provide verification of the source of their laboratory numbers or if the source is greater than 12 months (+3-month window) prior to completing the Web App, then the subject will be sent for study mandated testing for Triglycerides, TC, LDL-C, HDL-C and, if necessary, hs-CRP. If subject is not able to get to one of the local testing sites, the Call Center can direct them to order a home test kit. Subjects will not pay for study mandated testing. Subjects also have the option of rescheduling their appointment to locate their verified source. There will be no option to obtain CAC imaging in the event a subject inputs this information into the Web App and does not have a verified source at the virtual site visit. This CAC data will be documented as “unverified” but will be considered acceptable for use by the CMOG clinician for their TASS assessment if necessary. A missing CAC score would not exclude a participant from proceeding to participate in the AUS. (Note that is highly unlikely that a participant would understand a CAC score and enter a valid score into the Web App without having had the imaging test.) Women of childbearing potential will take an over-the-counter urine pregnancy test provided by the CRO prior to the virtual visit. At Virtual Visit 2, participants will be asked to verify the LDL-C entered into the Web App. If the participants did not provide verification or did not retest, then the participant will be sent for study mandated testing. See Section 8, Step 22 for a description regarding which participants are sent for study mandated testing. Women of childbearing potential will take another over-the-counter urine pregnancy test provided by the CRO.

8.3.5 Other Safety Assessments

When the participant completes the Web App to reorder, the Web App will ask questions about certain changes in health. Changes in health will also be assessed at each interim phone call.

8.4 Adverse Events and Serious Adverse Events

The Principal Investigator (PI) is responsible for ensuring that all staff involved in the study are familiar with the content of this section.

The definitions of an AE or serious AE (SAE) can be found in [Appendix B](#).

If the participant reports an AE, the investigator and any designees are responsible for detecting, documenting, and recording events that meet the definition of an AE.

8.4.1 Time Period and Frequency for Collecting AE and SAE Information

Adverse Events will be collected from the time of signature of informed consent form, throughout the use period and 30-days after study drug completion/discontinuation. All AEs will be followed to resolution.

SAEs will be recorded from the time of signing of informed consent form.

If the investigator becomes aware of an SAE with a suspected causal relationship to the investigational medicinal product that occurs after the end of the clinical study in a participant treated by him or her, the investigator shall, without undue delay, report the SAE to the sponsor.

8.4.2 Follow-up of AEs and SAEs

All AEs will be followed to resolution. AstraZeneca retains the right to request additional information for any participant with ongoing AE(s)/SAE(s) at the end of the study, if judged necessary.

Adverse event variables

The following variables will be collected for each AE:

- AE (verbatim)
- The date when the AE started and stopped
- Severity
- Whether the AE is serious or not
- Investigator causality rating against the Investigational Product(s) (yes or no)
- Action taken with regard to Investigational Product(s)
- AE caused participant's withdrawal from study (yes or no)
- Outcome

In addition, the following variables will be collected for SAEs:

- Date AE met criteria for SAE
- Date investigator became aware of SAE
- AE is serious due to
- Date of hospitalization

- Date of discharge
- Probable cause of death
- Date of death
- Autopsy performed
- Causality assessment in relation to Study procedure(s)
- Causality assessment to other medication

